9.3.5 Temperature Excursions

All temperature excursions outside the storage conditions for Carfilzomib specified in the IB must be reported to LEEDS CTRU.

Upon identifying an excursion:

- all affected trial stock must be quarantined IMMEDIATELY
- the 'Notification of Temperature Excursion' form must be completed and e-mailed to [contact] or faxed to [name].

Please note that LEEDS CTRU must be informed immediately if a patient has been administered drug affected by a temperature excursion.

9.4 Clinical Management after Treatment Discontinuation

Patients whose underlying plasma cell dyscrasia does not respond by the end of three cycles or who have a clonal progression on treatment will be treated and followed up off trial at the discretion of the treating clinician but will have a final follow-up visit 6 months after registration.

Patients that receive 6 cycles of chemotherapy will be followed up 1 month after end of trial treatment.

Also refer to section 14 (Withdrawal of Patients) for further details regarding treatment discontinuation, patient withdrawal from trial treatment and withdrawal of consent to data collection.

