11.0 Assessments

The trial consists of an initial treatment period of up to 6 cycles of chemotherapy treatment (approximately 7 months) for all patients. Follow up will be 6 months after registration or 1 month after the end of treatment if 6 cycles of chemotherapy was administered.

Trial data will be recorded by UK NAC and RHCs research staff on the CRFs and submitted to the LEEDS CTRU. It is the responsibility of each trial site to retain copies of all completed CRFs and to maintain their Investigator Site File which contains all essential documentation for the trial that is required at site.

5ml serum samples will be sent to the UK NAC by the RHCs for central testing as part of routine clinical practice; as noted in the following sections of the protocol. Packs, containing appropriately labelled sample tubes for the central testing associated with this trial, will be provided to participating RHCs by the UK NAC.

The central investigations are of key importance in relation to the in-depth assessment of the disease, prognostic factors, and the analysis of response to treatment and outcome.

See Trial Contacts at the beginning of the protocol for addresses for sending samples for central analysis and CRFs.

Assessment summary table:

Investigation	Baseline (Registration at UK NAC)	Re- confirmation of Eligibility (at RHC) ^e	Treatment			Prior to beginning of 4 th Cycle (at UK NAC)	End of treatment visit (at RHC)	Follow up visit (at UK NAC)
			Carfilzomib and Dexamathasone days 1, 8, 15		Thalidomide days 1-28			
			Prior to each treatment cycle (at RHC) ^f	Day 8				
Informed consent	X							
Patient details (including initials, date of birth, sex)	X							
Medical History	X							
Physical Examination ^a	X	X	X			X	X	X
Laboratory tests ^b	X ^b	X	X	X ⁱ	X ⁱ	X	X	X ^b
Pregnancy test	X	X	X ^h			X	X	X ⁱ
Assessment of response at UK NAC						X		X
Echocardiography incl. Tissue Doppler	X		X ^g			X ^g		X
24 Hour Holter monitor	X							
Bone marrow examination ^c	X							
Adverse Events	X	X	X	X	X	X	X	X
Concomitant Medication	X	X	X	X	X	X	X	X
Hepatitis B test	X							
5ml serum sample to UK NAC ^d Used to assess response to treatment			On Day 1 of treatment cycle 1, 2, 3, 5, 6 (to be taken at RHC and sent to UK NAC) AND within a week of the planned start date of the 4 th cycle					

^a Including height, weight, lying and 5 minute standing blood pressure, ECOG performance status

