The continuation of chemotherapy in this trial beyond the third cycle depends on assessment and classification of response at the end of the third cycle of treatment. An Investigator at the UK NAC will send a confirmatory letter from the UK NAC about the classification of response and further treatment though treatment for the next cycle may commence immediately if indicated.

Patients will be seen at the UK NAC after three cycles and either 6 months after registration or in patients receiving a full 6 cycles of chemotherapy, 1 month after the final cycle of treatment.

Thereafter, patients will be monitored off protocol as per their clinical need.

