14.1.1 Withdrawal due to clinical reasons

The site investigator may withdraw a patient from the trial treatment whenever continued participation is no longer in the patient's best interests, but the reasons for doing so must be recorded. Reasons for discontinuing treatment may include:

- Disease progression whilst on therapy
- Unacceptable toxicity
- Intercurrent illness which prevents further treatment
- The patient withdraws consent to further treatment
- Any alterations in the patient's condition which justifies the discontinuation of treatment in the site investigator's opinion

In these cases patients remain within the trial for the purposes of follow-up and data analysis according to the treatment option to which they have been allocated and for allowing existing collected data to be used. If the patient gives a reason for their withdrawal, this should be recorded.

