18.3 Endpoint definitions

- DLT and MTD are defined in section 8.1.4 and 8.1.5
- The proportion of patients treated who experience any grade 3 or 4 CTCAE toxicity will be calculated as number of patients who experience any grade 3 or 4 CTCAE toxicity throughout their treatment cycle.
- Clonal response rate (based on paraprotein and FLCs) is defined as the proportion of patients who achieve at least a PR within 3 months, at 3 months, within 6 months and at 6 months after trial registration.
- Amyloidotic organ response rate is defined as the proportion of patients who achieve organ response within 3 months and within 6 months of trial registration.
- Time to Amyloidotic organ response is defined as the time from the dose allocation to first achieving organ response.
- The number of patients experiencing dose delays will be defined as the number of patients experiencing delays in treatment with any of the study treatments.
- KTD compliance: Patients will be regarded as compliant to treatment where treatment is received as per protocol until withdrawal from treatment and have no more than 1 dose omission of Carfilzomib, 5 of Thalidomide or 1 of Dexamethasone during each cycle.
- Relative Dose intensity will be calculated as the percentage ratio between the received and planned dose intensities, where dose intensity is the cumulative dose divided by the duration of treatment.

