19.0 Statistical considerations

19.1 Sample size

In the dose escalation phase of this study, a minimum of 6 (3 at dose level 0 and 3 at dose level -1) and a maximum of 18 (6 at dose level 0 1 and 2) patients will be recruited in a 3+3 design with cohorts of between 3 and 6 patients, in order to determine maximum tolerated dose and recommended dose.

At the recommended dose level identified, a further 20 patients will be recruited to further assess safety and toxicities at the RD.

The secondary objective of assessing activity will be primarily assessed by the clonal response rate.

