APPENDIX 6 CONTINUED FROM PREVIOUS PAGE

Other investigations to be performed at UK NAC at the following timepoints:

- PLEASE NOTE – prior to starting each cycle at RHC a 5ml serum sample must be collected and sent to UK NAC
- * Baseline at UK NAC, at UK NAC visit following 3rd cycle of study treatment, at UK NAC visit 6 months after registration or 1 month after the end of study treatment if 6 cycles given and on posted serum samples and on each posted sample sent by RHC as defined in protocol
- ** Baseline visit to UK NAC and at UK NAC visit 6 months after registration or 1 month after the end of study treatment if 6 cycles given. Bone marrow tests will be done at these time points only if clinically indicated.
- *** Baseline at UK NAC, at UK NAC visit following 3rd cycle of study treatment, at UK NAC visit 6 months after start of treatment or 1 month after the end of study treatment if 6 cycles given. At RHC ECHO will be done at end of cycle 2 only. Echocardiogram to be repeated at any cycle if clinically indicated for unexpected worsening of cardiac function.
- **** Baseline at UK NAC, 1st cycle of treatment at day 1, 8 & 15 at RHC, day 1 of every subsequent cycle at RHC, at UK NAC visit following 3rd cycle of study treatment, at RHC at end of treatment, visit, at UK NAC visit 6 months after registration or or 1 month after the end of study treatment if 6 cycles given.
 - Serum Free Light Chains*
 - NT-ProBNP****
 - Echocardiography ***
 - Bone marrow aspirate & trephine plasmacytosis**
 - 24 hour urinary light chain type and quantification**
 - Serum monoclonal protein*

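### The 6-month clonal response rates have no rule for later therapy, so read literally they can count a PR reached on the next regimen as a KTD response

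*Protocol*

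**What the plan says.** Protocol 18.3 defines the clonal response rate as the share of patients reaching "at least a PR within 3 months, at 3 months, within 6 months and at 6 months after trial registration". SAP 2.3.2 repeats this and adds no derivation rule. Protocol 19.1 gives the endpoint its role: "The secondary objective of assessing activity will be primarily assessed by the clonal response rate".

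Continuing KTD beyond cycle 3 "depends on assessment and classification of response at the end of the third cycle of treatment" (Protocol 11.2). Protocol 9.4 sets out what happens to patients whose clone has not responded by then, or who progress clonally during KTD: "treated and followed up off trial at the discretion of the treating clinician but will have a final follow-up visit 6 months after registration".

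Response is measured at that visit. The Protocol 11.0 summary table marks the row "Assessment of response at UK NAC" at the UK NAC follow-up visit. Appendix 6 schedules serum free light chains and monoclonal protein at "Baseline at UK NAC, at UK NAC visit following 3rd cycle of study treatment, at UK NAC visit 6 months after registration", among other times.

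Patients taken off treatment for clinical reasons, disease progression included, "remain within the trial for the purposes of follow-up and data analysis according to the treatment option to which they have been allocated" (Protocol 14.1.1).

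**The concern.** The stated aim is to assess the activity of KTD. A patient who fails three cycles, starts another regimen and reaches PR by month 6 is a KTD failure, yet meets the written definition of a 6-month responder. The same holds for a patient who progresses on KTD and regains a PR on the next regimen, for the at-6-month rate. Patients who stop KTD for toxicity and are then treated with something else raise the same question.

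Clonal response is the main measure of activity, and Protocol 3.1 says that the expansion cohort should help in designing further trials. If next-line responses enter the numerator, the 6-month rates carried into that planning are too high.

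**Working it through.** **Does any provision close the gap?**

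- *Endpoint definition.* Registration is the only clock, and current treatment is not mentioned. By contrast, SAP 5.3.2 tabulates maximum clonal response within six cycles of treatment.
- *Per-protocol set (SAP 3.3).* It removes patients with no carfilzomib dose, no post-baseline efficacy assessment, or a deviation relevant to efficacy. A switch under Protocol 9.4 follows the protocol, so it is not in itself a deviation. Excluding these patients would also raise the rate, because KTD failures would leave the denominator.
- *Subsequent therapy.* Neither document has a censoring rule, a non-responder rule or a last-assessment-on-KTD rule.

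**Is there time to respond on a new regimen?**

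The visit at the regional centre may fall up to 28 days after registration, and treatment may start up to 6 weeks (42 days) after the eligibility form (Protocol 7.1). The longest lead is therefore 28 + 42 = 70 days. Three 28-day cycles take 84 days, and 6 months is taken as 183 days. The window for new therapy after cycle 3 is

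w = 183 − 84 − lead − other delay.

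**How large could the effect be?**

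The plan states no target response rate, so there is no figure of its own to reproduce. Inputs:

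- N = 26: six patients at the RD from escalation (Protocol 8.1.3) plus 20 in expansion (19.1).
- KTD response p = 60%: an assumption with no source in the documents.
- Next-line response s = 41% (lenalidomide-dexamethasone) or 48% (pomalidomide), both from Protocol 2.1.2.
- Time to response: assumed exponential, with the 1.9-month (57.8-day) median given for pomalidomide in Protocol 2.1.2.
- Share of patients below PR who switch: 1 or 0.5, assumed. Appendix 4 lists MR separately from no response, so some patients below PR may stay on KTD.

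Fraction of eventual next-line responders seen in the window: f(w) = 1 − 0.5^(w/57.8).

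Extra responders = N × (1 − p) × share × s × f(w). For 71 days, full switching and s = 41%: 26 × 0.40 × 1 × 0.41 × 0.573 = 2.44 patients, and 2.44/26 = 9.4 points.

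| Lead and delay | w (days) | f(w) | All switch, s = 41% | Half switch, s = 41% | All switch, s = 48% |
|---|---|---|---|---|---|
| 28-day lead | 71 | 0.573 | 2.44 (9.4 points) | 1.22 (4.7) | 2.86 (11.0) |
| 28-day lead, 21 days to next therapy | 50 | 0.451 | 1.92 (7.4) | 0.96 (3.7) | 2.25 (8.7) |
| 70-day lead | 29 | 0.294 | 1.25 (4.8) | 0.63 (2.4) | 1.47 (5.6) |
| 70-day lead, 14 days to next therapy | 15 | 0.165 | 0.70 (2.7) | 0.35 (1.3) | 0.82 (3.2) |
| 70-day lead, two 14-day cycle delays | 1 | 0.012 | 0.05 (0.2) | 0.03 (0.1) | 0.06 (0.2) |

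The shift is proportional to 1 − p. The largest cell would be 0.70 × 0.48 × 0.573 = 19 points at p = 30%, and 0.30 × 0.48 × 0.573 = 8 points at p = 70%. Patients who start within 28 days of registration, or who progress before the end of cycle 3, have more time left and are not modelled.

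For scale, the exact (Clopper-Pearson) 95% interval for 16/26 is 40.6% to 79.8%.

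**The case against.** The strongest reply is that no passage says an off-trial PR counts. Protocol 9.4 places later treatment and follow-up off trial. The retained visit also serves other endpoints, namely deaths and progression-free status at 6 months. Protocol 14.1.1 keeps patients in the analysis without saying how a response on another drug is classified. All of this stands. A reader might infer that the plan deliberately credits next-line responses to KTD. The documents do not support that; they are silent. The silence still matters, because a programmer following the written definition would count the PR.

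Second, Protocol 19.1 names clonal response without a time point, and on-treatment measures appear beside the 6-month rates: maximum response within six cycles, the largely unaffected 3-month rates, and reasons for stopping. This limits the harm but does not correct the 6-month figures.

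Third, the size is driven by assumptions. With half switching and a 70-day lead it is about 2 points or less, under one patient in 26. A reader who picks a next-line response rate freely, ignoring the calendar, could reach shifts of several tens of points. The documents do not support such figures, because the time left after cycle 3 is short.

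Fourth, bias in organ response has little practical support. The wording gap is the same, but the carfilzomib AL amyloidosis study in Protocol 2.1.3.4 saw no organ responses at a median follow-up of 5.1 months, and no figure here estimates the effect.

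**Conclusion.** The gap holds as an unspecified rule for subsequent therapy in the within-6-month and at-6-month clonal response rates. For patients who switch without a PR, the literal definition can only add responders. Confidence is high in the wording and low in the size. The illustration of about 0 to 11 points rests on an unsourced 60% KTD rate, borrowed next-line figures, assumed switching shares and leads of 28 to 70 days. The tabulated shifts are smaller than the sampling uncertainty at 26 patients, but a confidence interval does not remove a bias.

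A reader might infer that the trial's main conclusions are at risk. They are not. The endpoint is secondary and descriptive, no test or sample size depends on it, and the MTD and RD rest on first-cycle DLTs. It should be fixed because the definition as written points the wrong way and the correction costs little.

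**What to change.** Amend Protocol 18.3 and SAP 2.3.2:

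1. Count a clonal response within 6 months only if it is first documented before the start of any non-protocol anti-clonal therapy.
2. For the at-6-month rate, count as non-responders all patients who started such therapy before the assessment. Show separately the number who switched while still in a KTD-induced PR. Keep all of them in the denominator.
3. Report response regardless of later therapy as a sensitivity analysis.
4. Take the start date of the next therapy from the "Concomitant Medication" record, already scheduled at the follow-up visit (Protocol 11.0), and confirm that the form captures it.

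For consistency, apply the same rule to the 6-month organ response rate. In time to organ response, treat the start of new therapy as a competing event. Censoring there would be informative, because patients switch for lack of response.

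The cost is wording in two places and a check that one date is captured. Clinical management does not change. The 6-month rates may look slightly less favourable, partly because item 2 also counts patients who switch while in PR as non-responders; showing their number lets the reader judge that.

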9.5 Out-of-hours medical care

Medical care, including out-of-hours medical care is the responsibility of the site. Sites must ensure that all patients registered onto the have received a CATALYST patient card and Red Flag card (which lists symptoms needing immediate medical attention) with out-of-hours contact details.

10.0 Dose delays and modifications

The dose of Carfilzomib should be delayed and / or reduced according to the guidelines given below (CTCAE v4.03). Dose re-escalation may occur if the toxicities were considered to be disease related, however dose re-escalation should only be undertaken following discussion with the CI.

Please see appendix 8 for known risk and discomforts from Carfilzomib.

10.1 Cycle 1 - dose escalation phase only

If toxicity occurs between day 1 of cycle 1 and first dose of treatment administered in cycle 2 treatment of the dose escalation phase, please refer to Section 8.1.4 for DLT definitions.

Any patient experiencing a DLT during cycle 1 of the dose escalation phase will have his or her treatment withheld until toxicity resolves to baseline or Grade ≤ 1 . Upon resolution, the patient may have therapy re-instituted at the next lowest dose level, unless this occurs dose level -1, where patients will stop therapy.

If a patient experiences an SAE or grade 3/4 toxicity after the day 1 dose of cycle 1 (loading carfilzomib dose) treatment should be delayed until toxicity has resolved to baseline or Grade ≤ 1 and then discussed with the CI to see whether it is safe to proceed as planned.

If there is a greater than 8 day delay in dosing due to toxicity attributable to the loading dose of Carfilzomib, the safety review committee will be notified.

10.2 Subsequent cycles (all patients)

In summary treatment should be delayed for any patient experiencing:

- Grade 4 thrombocytopenia with active bleeding
Grade 4 anaemia and Grade 4 thrombocytopenia (without active bleeding) do not require the Carfilzomib dose to be withheld. Participants should receive supportive measures in accordance with institutional guidelines.
- Grade 4 neutropenia or neutropenic fever
- Grade 3/4 non-haematological toxicity

Treatment should continue to be withheld until the neutrophil count and platelet count return to $\geq 0.75 \times 10^9/L$ and $\geq 25 \times 10^9/L$, respectively (during a cycle). Drug-induced non-haematological toxicities have to have reached baseline, or become Grade ≤ 1 prior to re-treatment. Treatment may be delayed up to 8 days to allow sufficient time for recovery from toxicities. Please check table 3 and table 5 for dose reduction guidelines.

If the haematological or non-haematological AE has not resolved within 14 days the patient must discontinue from therapy, if the haematological or non-haematological toxicities have resolved within 14 days, the patient may have their therapy re-instituted at the next lowest dose level. Please check table 3 and table 5 for dose reduction guidelines.

A dose delay of up to 14 days (up to 3 weeks for infection treatment) is permitted at the beginning of a cycle to allow resolution of toxicity. If there is no resolution of toxicity as stated above after 2 weeks of withholding treatment (3 weeks for infection treatment), the participant will be discontinued from treatment. Withholding treatment for more than 2 weeks for other reasons, eg elective surgery such as vertebroplasty, may be permitted after discussion with the CI.

No more than three dose reductions or delays in two consecutive cycles will be permitted in an individual participant on study. If toxicity continues or recurs after three dose reductions or delays, the participant should be discontinued from treatment.

If a patient vomits after taking a dose of an oral agent, no repeat dose should be taken and patient will continue as per schedule but the clinical team should consider prophylactic antiemetics.

All previously established or new toxicities observed at any time, with the exception of neuropathic pain and peripheral sensory neuropathy, are to be managed as detailed in table 3 recommended action for haematologic toxicities and table 5 dose adjustment guidelines for non-haematological toxicities.

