10.3 Haematological Parameters

The following parameters must be met on the **first day of a new cycle** (other than cycle one, when the inclusion for initial registration parameters must be met):

- Platelet count $\geq 50 \times 10^9/L$, Haemoglobin $\geq 8g/dl$, (prior red blood cell transfusion or recombinant Human Erythropoietin usage is allowed), ANC $\geq 1 \times 10^9/L$.

On any day of Carfilzomib administration **during a cycle** (other than day one of each cycle), the haematological results must be:

- Platelet count $\geq 25 \times 10^9/L$, Haemoglobin $\geq 8g/dl$ (prior red blood cell transfusion or recombinant Human Erythropoietin usage is allowed), ANC $\geq 0.75 \times 10^9/L$.

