10.4 Dose Reduction For Haematologic Toxicities

Patients will have a FBC prior to each dose of Carfilzomib during treatment.

Carfilzomib will be withheld from participants with:

- Grade 4 thrombocytopenia with active bleeding
- Grade 4 neutropenia

The following table outlines the dose reduction guidelines for Carfilzomib for thrombocytopenia and neutropenia:

Table 3: Recommended Action for Haematologic Toxicities

Haematologic Toxicity	Recommended Action	
Thrombocytopenia		
When platelets fall to $\leq 25 \times 10^9 / L$	If platelets $10 - 25 \times 10^9 / L$ without evidence of bleeding	Continue at same dose
	If evidence of bleeding or platelets $< 10 \times 10^9 / L$	Withhold dose until platelets return to $\geq 10 \times 10^9 / L$ and/or bleeding is controlled, then resume at same dose.
For each subsequent drop to $\leq 25 \times 10^9 / L$	If platelets $10 - 25 \times 10^9 / L$ without evidence of bleeding	Continue at same dose
	If evidence of bleeding or platelets $< 10 \times 10^9 / L$	Withhold dose until platelets return to $\geq 10 \times 10^9 / L$ and/or bleeding is controlled, then resume at 1 dose decrement
Neutropenia		
When ANC falls to $\leq 0.75 \times 10^9 / L$	If ANC $0.5-0.75 \times 10^9 / L$	Continue at same dose

	If ANC $< 0.5 \times 10^9 / L$	Withhold dose until ANC returns to $\geq 0.5 \times 10^9 / L$, then resume at same dose.
For each subsequent drop to $\leq 0.75 \times 10^9 / L$	If ANC $0.5-0.75 \times 10^9 / L$	Continue at same dose
	If ANC $< 0.5 \times 10^9 / L$	Withhold dose until ANC returns to $\geq 0.5 \times 10^9 / L$, then resume at 1 dose decrement.
Neutropenic fever	If $< 1000/mm^3$ and single temperature $> 38.3^{\circ}C$ OR temperature $> 38.0^{\circ}C$ for more than one hour.	Withhold dose until ANC returns to baseline grade, then resume at same dose.

Please note; if doses of carfilzomib need to be delayed then the dexamethasone dose must also be delayed so that it can be taken prior to the carfilzomib dose. Thalidomide can be taken continuously unless there is toxicity directly attributable to Thalidomide.

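### From cycle 2 on, Protocol 10.2 and 10.3 disagree on whether carfilzomib must be held in grade 4 anaemia when haemoglobin is still below 8 g/dL after support

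*Protocol*

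**What the plan says.** Protocol 10.2 covers all patients in cycles after the first. It says "Grade 4 anaemia and Grade 4 thrombocytopenia (without active bleeding) do not require the Carfilzomib dose to be withheld", and asks for supportive care under institutional guidelines. Its criteria for restarting during a cycle name neutrophils (0.75 x 10^9/L) and platelets (25 x 10^9/L) but not haemoglobin.

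Protocol 10.3 sets blood-count conditions for dosing. Its rule for day 1 of a new cycle opens "The following parameters must be met on the". Its rule for other carfilzomib days applies on any such day "other than day one of each cycle), the haematological results must be" at the listed values. Both rules list haemoglobin of at least 8 g/dL, with the allowance "prior red blood cell transfusion or recombinant Human Erythropoietin usage is allowed". Neither section mentions the other.

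The end of 10.2 says that toxicities "are to be managed as detailed in table 3 recommended action for haematologic toxicities". Section 10.4 introduces Table 3 as follows: "The following table outlines the dose reduction guidelines for Carfilzomib for thrombocytopenia and neutropenia". The table has no anaemia row.

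**The concern.** A patient with grade 4 anaemia may still be below 8 g/dL on the dosing day despite transfusion or erythropoietin. A site reading 10.2 may treat this patient as exempt from a hold, while a site reading 10.3 will hold. With 15 planned sites, the same patient could be handled in two ways. What is at stake is consistent and safe dosing of a frail patient and, to a very small degree, the descriptive summaries of delays and dose intensity.

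**Working it through.** The plan gives no figure to reproduce, so the main check is to set the rules side by side.

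| Situation, cycle 2 or later | 10.2 | 10.3 |
|---|---|---|
| Anaemia below grade 4, haemoglobin under 8 g/dL | silent | dosing condition not met |
| Grade 4 anaemia, raised to 8 g/dL or more by support | no hold required | dosing condition met |
| Grade 4 anaemia, still under 8 g/dL on the dosing day | no hold required | dosing condition not met |

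Only the last row is a disagreement. It is framed by the haemoglobin value itself, so it does not depend on the CTCAE grade 4 definition for anaemia, which Appendix 5 does not reproduce.

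**Does other text rank the two sections?**

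- Table 3 covers thrombocytopenia and neutropenia only.
- The list in 10.4 of reasons to withhold omits anaemia, which leans towards 10.2.
- The list in 10.11 of conditions that need no hold also omits anaemia, which leans towards 10.3.
- Section 10.12 asks for anaemia to be corrected but gives no threshold.
- The SAP is silent.

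**Can a site assume that 10.3 always prevails?** Table 3 says "Continue at same dose" for platelets of 10-25 without bleeding and for neutrophils of 0.5-0.75 (x 10^9/L). Apart from the upper end points, those ranges lie below the mid-cycle limits in 10.3 (25 and 0.75). They lie wholly below its day 1 limits (50 and 1). If 10.3 always governed, those rows would have almost no effect.

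**Does the disagreement reach the DLT window?** DLTs are collected in the escalation phase up to the first dose of cycle 2. Section 10.1 covers that interval, and 10.2 covers later treatment. On that reading the disputed sentence is not in force while DLTs are counted.

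**Size for one affected patient.** Assume 6 cycles of 28 days, so 168 planned days, with every dose eventually given. Relative dose intensity = 168 / (168 + days held).

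- 1-day hold: 168/169 = 99.4%
- 8-day hold: 168/176 = 95.5%
- 14-day hold at the start of a cycle: 168/182 = 92.3%

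If a full dose is omitted instead, the planned total is 20 + 17 x level. At 36 mg/m² that is 632 mg/m², and 596/632 = 94.3%. Across the four levels the range is 94.2% to 94.4%.

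**Size for the RD cohort.** Take 6 + 20 = 26 patients. One such patient moves mean relative dose intensity by 0.6/26 = 0.02 points (1-day hold) to 7.7/26 = 0.30 points (14-day hold). The proportion with a delay moves by 1/26 = 3.8 points.

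**The case against.** The best counter-argument is that both rules can be obeyed. Section 10.2 only permits: it says a hold is not required and never tells a site to dose. Section 10.3 is mandatory. Holding below 8 g/dL breaches neither section, while dosing below 8 g/dL breaches 10.3 as worded. Section 10.2 presents its list as a summary, and its mid-cycle restart limits for neutrophils and platelets equal those in 10.3, which suggests that the two were meant to be read together. There are safeguards too: "Patients will have a FBC prior to each dose of Carfilzomib during treatment", section 17.1 requires deviations to be reported and lets unsure staff ask the trials unit, and SAP 4.1 lists protocol deviations among the items examined continuously.

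Most of this stands. A reader might infer that the protocol directs sites to dose below 8 g/dL, or that no compliant action exists. The documents support neither reading. What remains is that the two sections differ on whether a hold is required, that the sensible reading has to be inferred, and that Table 3 weakens the inference by departing from 10.3 for the other two counts. Table 3 does not itself say which rule applies to haemoglobin. The route to the trials unit helps only a site that notices the question.

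**Conclusion.** The disagreement is real but narrow, and of minor severity. It is confined to grade 4 anaemia, from cycle 2 on, with haemoglobin still below 8 g/dL on a carfilzomib day. Section 10.3 is the safer and more natural gate, but this should be stated.

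A reader might infer that dose finding is affected. It is not, provided that 10.1 is taken as the rule up to the first cycle 2 dose in the escalation phase, as its text indicates. No effect on DLTs, the MTD or the RD is claimed. The effect on dose-intensity summaries is negligible: at most 0.30 points on the mean per affected patient, given 26 patients, six planned cycles and a hold of no more than 14 days.

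The case is probably rare, but its frequency cannot be estimated from the documents. A reader might try to bound it from the AL amyloidosis study in 2.1.3.4, where no anaemia of grade 3 or higher is listed among 11 evaluable patients. That list may not be exhaustive, the schedule was twice-weekly carfilzomib (two patients had dexamethasone added), and the case here is a smaller subset. A bound built on it would tell us nothing useful.

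**What to change.** In 10.2, replace the anaemia part of the sentence with: *For grade 4 anaemia, give supportive measures; carfilzomib is given only once haemoglobin is at least 8 g/dL (section 10.3; transfusion or erythropoietin allowed), and is then resumed at the same dose. The 14-day limit on unresolved toxicity in this section still applies.*

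Add a matching anaemia row to Table 3. Stating the restart dose matters because 10.2 otherwise allows restart at the next lower level once toxicity has resolved within 14 days. State also whether such holds count towards the 10.2 cap of three reductions or delays in two consecutive cycles.

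In the same amendment, say whether 10.3 or Table 3 governs platelets of 10-25 and neutrophils of 0.5-0.75, both on day 1 and mid-cycle. Align the 10.2 wording on grade 4 thrombocytopenia without bleeding with that choice. A correction for haemoglobin alone would leave the same kind of mismatch there.

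The cost is a protocol amendment with approvals as appropriate (section 21.4) and notice to sites. No new test is needed, because a blood count already precedes each dose, and section 19.4 already summarises reasons for delays. The downside is possibly a few short delays. These may count towards the cap or, if anaemia is refractory beyond 14 days, lead to discontinuation.
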